### 16.3.2. ANALYSIS OF EXPLORATORY VARIABLES

Data will be summarized for all patients in the ITT population, by treatment group.

For the endpoint #1, the comparisons between groups on glucagon in terms of basal to 180 min time course will be carried-out using a mixed linear model with glucagon derived from the MMTT as dependent variables, treatment group, visit, time, treatment by visit interaction, time by visit interaction and treatment by time by visit interaction as fixed factors of the model and patient as random effect. An unstructured covariance matrix for each patient is considered and the Kenward-Roger adjustment is used for the degrees of freedom. Furthermore, default summary statistics of Cmax and Tmax of the MMTT at each visit will be provided. Cmax and Tmax will be calculated up to 180 minutes after mixed meal administration (time interval ranging from 15 min. to 180 min.).

For the endpoints from #2 to #4 default summary statistics of the values over time and the changes from baseline will be provided.

For the endpoint #5, the comparisons between groups will be carried-out using a mixed linear model with 2-hour AUC of C-peptide response to the MMTT as dependent variable, treatment group, visit, number of positivity in auto-antibodies at Screening visit, treatment by visit interaction, treatment by number of positivity interaction as fixed factors of the model and patient as random effect. An unstructured covariance matrix for each patient is considered and the Kenward-Roger adjustment is used for the degrees of freedom.

Analysis of endpoint #6 will be performed calculating the number and proportion along the 95% confidence interval (Clopper-Pearson's formula) of patients responder. The comparison between the two study treatment arms will be performed by means of a Chi-square test or, if more appropriate, a Fisher's Exact test.

### 16.3.3. POST-HOC AND SUBGROUPS ANALYSES

Post-hoc and subgroups analyses aiming to compare the two treatment groups might be considered for all the efficacy endpoints. Such analyses might include, but may not be limited to, calculation of additional endpoints (e.g., Igl score and/or beta2 score), subgroup analysis of efficacy variables by time from first insulin dose to randomization, i.e.  $\leq 6$  weeks and  $\leq 10$  weeks). Descriptive and appropriate inferential statistical tests will be used. The reason to perform such post-hoc and subgroups analyses will be presented and justified in an appropriate document before to perform the analysis.

Document: MEX0114\_SAP\_v4\_4 Final Methods.docx  
 Author: [name]

Version Number:  
 Version Date:

Final Version 4.4  
 [17SEP2019]

Template No: CS\_TP\_BS016 – Revision 4  
 Effective Date: 01Apr2016

Reference: CS\_WI\_BS005

## 16.4. SAFETY ANALYSES

### 16.4.1. SAFETY VARIABLES

The safety analyses will include the following variables:

1. Vital signs (SBP, DBP and heart rate)
2. Routine laboratory tests (hematology, clinical chemistry)
3. Incidence of Treatment Emergent Adverse Events (TEAEs) and Treatment Emergent Serious Adverse Events (TESAEs)

### 16.4.2. ANALYSIS OF SAFETY VARIABLES

Data will be summarized for SAF set with descriptive statistics, by treatment group.

Default summary statistics of vital signs and results for routine laboratory tests over time and the changes from baseline will be provided. Vital signs (SBP, DBP and heart rate) will be recorded at baseline, at pre-dose visit of 2nd cycle and at week 13±1 follow-up visit. Routine laboratory tests will be performed at baseline, pre-dose visit of 2nd cycle and at week 13 ±1 follow-up visit only.

Moreover, results for routine laboratory tests will be assessed as being below the lower limit of the normal range, within the normal range or above the upper limit of the normal range and will be summarized with a frequency table for each visit.

The frequency of patients reporting an abnormal (not clinically significant or clinically significant) laboratory value at Screening and at subsequent visits will be presented for each laboratory variable.

TEAEs will be presented in terms of the number of TEAEs, the incidence, severity and relationship to the study drug, overall and by System Organ Class and Preferred Term. TESAEs will be presented in the same way.

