2.5.1. Selection of dose and treatment schedule in the study

The proposed dose in this clinical study is 400 mg oral ladarixin twice a day for 3 cycles of 2 weeks on - 2 weeks off.

The oral route has been selected as the more appropriate for a 14 day continuous treatment. The PK profile support this choice.

The 400 mg dose has been selected to provide a drug exposure that would maximise the potential to observe a drug effect, while remaining within safety margins. Indeed, this dose was already established to be safe in phase 1 clinical studies in adult male healthy subjects. This dose will provide an average steady state plasma concentration of the ladarixin unbound fraction (about 100-150 ng/mL) that should ensure full inhibition of PMN migration, considering that the in vitro IC_{50} is in the range of 1 ng/mL.

The proposed treatment schedule (3 cycles of 14 days on - 14 days off) is intended to expose the patient to ladarixin for a period sufficient for such a molecule to establish a potential effect. According to International Conference on Harmonization (ICH) guidelines (guidance on non-clinical safety studies for the conduct of human clinical trials and marketing authorization for pharmaceuticals), the available repeated dose toxicity studies (4 weeks in rodents and dogs) support the conduct of phase 2 trials with a maximal exposure of 28 days. This proposed treatment schedule appears to exceed the duration of administration in previous clinical studies and in total will involve drug exposure over a longer period than has previously been explored in man or animals. However, each cycle of the proposed treatment can reasonably be regarded at this stage as a separate event that each is adequately supported by the available 28-day toxicity test results. Indeed, the PK in animals and man suggests clearance of the drug and its metabolites from the body of humans within 2-3 days at the most. Also, the pharmacodynamic studies in vitro and in vivo in animals and humans suggest reversibility of the effect on CXCR1/2 receptors within a short period after exposure to the drug has ceased.

The good safety profile of ladarixin in animals and humans further supports the proposed treatment schedule for this study.

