2.5.3.2. Blood sampling

Participation in the study will require additional blood samplings other than the routine ones. In particular:

- a blood sample (about 10 mL) will be obtained at screening, at the end of 1st treatment cycle (i.e. pre-dose visit, 2nd cycle) and at the 13 week follow-up visit to evaluate standard haematology and clinical chemistry;
- blood samples for diagnostic auto-ab test (maximum 5 mL) and for baseline auto-ab, HbA1c, miR-375, and MMTT c-peptide, glucose, glucagon (maximum 100 mL) will be taken during screening;
- blood samples (about 5 mL) will be obtained before the 3rd treatment cycle is started to monitor renal (creatinine) and hepatic (ALT/AST, bilirubin) function, and albumin;
- blood samples for auto-ab, HbA1c, miR-375 and MMTT c-peptide, glucose, glucagon (maximum 100 mL) will be taken during each of the 3 follow-up visits;
- T-cell response will require additional 10 mL of blood at the selected sites only.

Blood sampling will occur through a peripheral vein and may cause faintness and/or swelling, pain, redness, bruising, or infection (infection rarely happens) at the site where the needle is inserted. The volume of blood above is an amount that the body can safely replace.

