7.2.2. Pre-dose assessment - 2nd and 3rd treatment cycle

Patient will refer to the site within 1 week before the expected date when the 2nd or 3rd treatment cycle is due to start. The following will be evaluated:

- General clinical evaluation to ensure patients has not developed concurrent clinical conditions, including pregnancy in female participants, which in the opinion of the Investigator may pose a safety risk for continuing participation in the study
- Blood sampling(s) for measurement (local laboratories), of serum creatinine, serum albumin, total bilirubin, ALT, AST. Renal and hepatic function will be evaluated as per details in [Section 7.1.1](#) above.
- 12 lead ECG performed using local equipment that allows automatic calculation of the QTcF. If the QTcF is EITHER > 500 msec OR has increased by > 60 msec from baseline value, a second reading will be obtained 1 hour later.
- Pregnancy test (urine dipstick or blood sample), if appropriate.
- **On pre-dose 2nd cycle ONLY:** Measurement of blood pressure and heart rate; Blood sampling(s) will allow the measurement (local laboratories) of the whole set of “Safety Laboratory Tests” i.e.: hematocrit, hemoglobin, red blood cells, platelets, white blood cells, differential white blood cells count, sodium, potassium, serum creatinine, serum albumin, blood urea nitrogen, total bilirubin, ALT, AST.

Laboratory results and ECG reading MUST be made available before the Treatment Box for the next treatment cycles is dispensed.

As per discontinuation criteria (see [Section 6.3.2](#)), **no IMP will be dispensed** in the case:

- QTcF is either > 500 msec or increases by > 60 msec from screening measurement on two consecutive ECG readings taken 1 hour apart;
- The patient develops LBBB, or atrio-ventricular or heart block;
- The patient develops any significant cardiovascular disease;
- The patient develops renal (calculated CL_{cr} < 60 mL/min) or hepatic (increased ALT/AST > 3 x ULN and increased total bilirubin > 3mg/dL [$>51.3 \mu\text{mol/L}$]) dysfunction as well as hypoalbuminemia;
- Pregnancy occurs (female patient).

After having confirmed the patient has not developed a condition that prevents his/her continuing participation into the study, he/she will be provided with the Treatment Box - Cycle No. 2 or Treatment Box - Cycle No. 3 (as appropriate) matching his/her randomization number, together with the Diary Card.

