### 3.2.3. SAFETY ENDPOINTS

Vital signs (blood pressure and heart rate) [time points: Screening, end of 1st treatment cycle (i.e. pre-dose visit, 2nd cycle), week 13+1].

Routine laboratory tests (hematology, clinical chemistry) [time points: Screening, end of 1st treatment cycle (i.e. pre-dose visit, 2nd cycle), weeks 13±1 (or withdrawal)].

Incidence of Treatment Emergent Adverse Events (TEAEs) and Treatment Emergent Serious Adverse Events (TESAEs) [time frame: throughout the study].

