## 7.3. RETESTS, UNSCHEDULED VISITS AND EARLY TERMINATION DATA

No unscheduled visits have been foreseen in the study.

In general, for by-visit summaries, data recorded at the nominal visit will be presented. Unscheduled measurements will not be included in by-visit summaries.

Listings will include scheduled, unscheduled and early discontinuation data.

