#### 16.4.4. SAFETY LABORATORY EVALUATIONS

Results from the local laboratories will be included in the reporting of this study for Hematology and Blood Chemistry. Data will be summarized for the SAF set.

Presentations will use SI Units.

The following summaries will be provided for Hematology and Blood Chemistry laboratory data:

- 1) A summary table showing for all laboratory tests the values and changes from baseline to each subsequent visit by treatment group;
- 2) A summary table showing for all laboratory tests the frequency of patients reporting an out-of-range (below LLN or above ULN) laboratory value at Screening and at subsequent visits by treatment group.
- 3) A summary table showing for all laboratory tests the frequency of patients reporting an abnormal (clinically or not clinically significant) laboratory value at Screening and at subsequent visits by treatment group.

A listing showing values, the reference ranges and the clinical significance according to investigators' opinion will be produced. Laboratory data will be presented by-patient and within-patient by laboratory test and visit.

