## 16.7. PERMANENT TREATMENT DISCONTINUATION CRITERIA

Data will be summarized for the Safety Analysis Set (SAF).

The following measurements will be reported:

- IMP treatment completed (Yes/No)
- If No: total number of capsules administered
- If No: reason for permanent discontinuation of IMP:
  - QTcF > 500 msec or increased by 60 msec from Screening measurement on two consecutive ECG reading (1 hour apart)
  - Complete Left Bundle Branch Block (LBBB), atrio-ventricular block, complete heart block
  - Significant cardiovascular disease
  - Renal Dysfunction
  - Hepatic Dysfunction

---

Document: MEX0114\_SAP\_v4\_4 Final Methods.docx

Author: [name]

Version Number:

Final Version 4.4

Version Date:

[17SEP2019]

Template No: CS\_TP\_BS016 – Revision 4

Reference: CS\_WI\_BS005

Effective Date: 01Apr2016

Copyright © 2009, 2010, 2012, 2016 Quintiles Transnational Corp. All rights reserved.

The contents of this document are confidential and proprietary to Quintiles Transnational Corp. Unauthorized use, disclosure or reproduction is strictly prohibited.

- Hypoalbuminemia
- Pregnancy
- Other AE
- Other

The following listings of discontinuation criteria will be presented:

- Laboratory test results: Serum Creatinine, Serum Albumin, Total Bilirubin, ALT, AST (Screening, Pre-dose visit 2nd and 3rd cycle, for German Investigational sites only also Day 3-5 of 1st cycle).
- Creatinine Clearance (Screening, Pre-dose visit 2nd and 3rd cycle, for German Investigational sites only also Day 3-5 of 1st cycle).

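### On the most natural reading, the SAP lists but does not tabulate the liver, kidney and albumin results taken before cycle 3, and gives the withdrawal results no summary place

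*SAP*

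**What the plan says.** **Collection.** Protocol 7.2.2 covers the visits before cycles 2 and 3 and requires "Blood sampling(s) for measurement (local laboratories), of serum creatinine, serum albumin, total bilirubin, ALT, AST" at both. The full haematology and chemistry panel is added before cycle 2 only. Protocol 2.5.3.2 confirms the later draw: a small sample "will be obtained before the 3rd treatment cycle is started to monitor renal (creatinine) and hepatic (ALT/AST, bilirubin) function, and albumin". The full panel is repeated at week 13 (Protocol 7.3) and requested, where possible, at withdrawal (Protocol 7.4.1).

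**Endpoint.** The safety laboratory endpoint in Protocol 4.2.3 and SAP 3.2.3 is set at screening, the end of cycle 1 and "weeks 13±1 (or withdrawal"). Neither names the visit before cycle 3.

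**Analysis.** SAP 16.4.2 gives the routine laboratory schedule as baseline, before the second "cycle and at week 13 ±1 follow-up visit only". SAP 16.4.4 promises "A summary table showing for all laboratory tests the values and changes from baseline to each subsequent visit by treatment group", plus out-of-range and abnormality tables, without naming the visits. SAP 16.7 lists "Laboratory test results: Serum Creatinine, Serum Albumin, Total Bilirubin, ALT, AST (Screening, Pre-dose visit" of cycles 2 and 3), with creatinine clearance (CLcr) listed at the same visits. SAP 7.3 bases by-visit summaries on nominal visits and states: "Unscheduled measurements will not be included in by-visit summaries". It mentions early-discontinuation data only in its sentence on listings.

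**The concern.** Safety over repeated cycles is a real question in this trial. Protocol 2.5.1 supports three cycles by treating each as a separate event, while accepting that the schedule "in total will involve drug exposure over a longer period than has previously been explored in man or animals". Protocol 2.5.3.1 points to the monitoring in 7.2.2, laboratory tests included, as the way risk is kept low. One of the two laboratory visits in that section appears to reach no between-arm laboratory table.

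Reversible liver change is not a remote idea here. Protocol 2.2 reports hepatocellular hypertrophy in the 28-day rat study that resolved after two weeks off drug, and the adverse reaction table in 2.4.3 includes one abnormal liver function test. At stake is whether the tables could show a transient or modest shift after the second cycle, or any shift in patients who leave before week 13. Individual listings in a trial of 72 patients randomised 2:1 are a poor tool for seeing a group difference in ALT or creatinine.

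**Working it through.** The plan gives no figure on this point to reproduce. The check sets collected draws against tabulated ones and then lays out the nominal timing.

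**1. Collected against tabulated (creatinine, albumin, bilirubin, ALT, AST)**

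| Post-baseline draw | Collected (Protocol) | In SAP 16.4.2 schedule | In SAP 16.7 listing |
|---|---|---|---|
| Before cycle 2 | Yes (7.2.2) | Yes | Yes |
| Before cycle 3 | Yes (7.2.2, 2.5.3.2) | No | Yes |
| Week 13±1 | Yes (7.3) | Yes | No |
| Withdrawal | Where possible (7.4.1) | No, though named in SAP 3.2.3 | Not named |

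Of the three scheduled draws, two are tabulated and one is not: 1/3 = 33%. This leaves out the extra Day 3 to 5 draw at German sites, which SAP 16.7 also names only under listings. CLcr is named at baseline (SAP 11) and in the 16.7 listing; no post-baseline CLcr summary is specified at any visit.

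**2. Time off drug at each draw**

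Cycle k runs from day 1 + 28(k−1) to day 14 + 28(k−1): days 1–14, 29–42 and 57–70. Each pre-dose visit falls in the seven days before the next cycle starts.

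- Before cycle 2: days 22–28. Gap from the last cycle-1 dose: 22−14 = 8 to 28−14 = 14 days.
- Before cycle 3: days 50–56. Gap from the last cycle-2 dose: 50−42 = 8 to 56−42 = 14 days.
- Week 13±1, taken as day 7×12 = 84 to day 7×14 = 98. Gap from the last cycle-3 dose: 84−70 = 14 to 98−70 = 28 days.

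The last range depends on how weeks are counted. Counting week 12 from its first day (7×11+1 = 78) lowers the near end to 8 days. The target week itself, days 85–91, gives 15–21 days.

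On this timing, the draw before cycle 3 is the only one after repeated cycles that is scheduled at the same off-drug gap as the draw after cycle 1. The tables set one cycle against three, generally at a longer gap for the latter.

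**3. A patient who does not start cycle 3 but stays in follow-up**

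Protocol 6.3.2 and 7.4.1 ask such patients to remain. With a last dose on day 42, the next tabulated value comes 84−42 = 42 to 98−42 = 56 days later (36 days at the earliest on the wider week count).

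**4. What the other summaries capture**

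- SAP 16.7 summarises reasons for permanent discontinuation, including renal dysfunction, hepatic dysfunction and hypoalbuminaemia.
- SAP 16.4.3 tabulates TEAEs, and separately those leading to discontinuation.
- Neither necessarily captures a numeric shift that stays within the limits. The hepatic criterion in Protocol 6.3.2 needs both the transaminase and the bilirubin condition, so an isolated transaminase rise does not meet it. It reaches a TEAE table only if the investigator reports it as an adverse event.

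**The case against.** Several counter-arguments have weight.

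- **The exclusion is inferred.** The 16.4.2 sentence says when tests are performed, not what is tabulated. SAP 16.4.4 speaks of every later visit, the visit before cycle 3 is scheduled so 7.3 does not bar it, and the table shells, which fix the content, are not in the documents. This stands as a limit on certainty. It does not remove the conflict with the restrictive word in 16.4.2, or the fact that 16.7 names these values only for listings.
- **The SAP follows the protocol.** Protocol 4.2.3 also leaves the draw before cycle 3 out of the endpoint. That explains the gap, but it is no reason to leave collected data untabulated.
- **Withdrawal is ambiguous.** The wording in 3.2.3 may place the withdrawal sample in the week 13 slot, and 7.3 does not say that early-discontinuation data appear only in listings. A reader might infer that all withdrawal results are lost to the tables. The documents show only that no summary place is assigned.
- **The ECG contrast is weak.** SAP 16.5 does summarise QTcF from the visit before cycle 3, but no ECG is scheduled at week 13, so that is the last ECG. Laboratory tests have a later tabulated visit.

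Two stronger readings should be resisted. A reader might infer that the tables cannot show an effect that builds up over cycles. Week 13 follows all three cycles and is tabulated, so a lasting effect could appear there. A reader might also infer that a patient who crosses a liver or kidney limit before cycle 3 and recovers would look normal everywhere. Crossing a stopping limit leads to discontinuation, and its reason is summarised in 16.7.

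**Conclusion.** The point holds as a reporting gap. On the most natural reading of SAP 16.4.2 and 16.7, one of three scheduled post-baseline draws of five liver, kidney and albumin analytes is listed but not tabulated, and the withdrawal time point in SAP 3.2.3 has no stated place in the summaries. The consequence is reduced ability to see, between arms, a reversible or sub-threshold change after repeated cycles, or any change in patients who leave before week 13.

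The number leaving before week 13 cannot be taken from the documents. It is tempting to apply the 24% drop-out in the sample size section (0.24 × 72 = 17.3 patients). That is a planning allowance in a calculation based on 12-month data, and patients who stop treatment are asked to stay in follow-up, so it does not estimate early exits.

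The timing argument assumes nominal dosing days and week 13±1 at days 84–98. The primary efficacy analysis is unaffected, and no result is lost from the record.

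**What to change.** 1. In SAP 16.4.2 and 16.4.4, add the visit before cycle 3 to the change-from-baseline, out-of-range and abnormality tables for creatinine, albumin, bilirubin, ALT and AST, and summarise CLcr at the visits where it is already listed.
2. Add one worst post-baseline row per analyte, by treatment group, using scheduled, unscheduled and withdrawal results, and state in 7.3 that this row is exempt from the nominal-visit rule.
3. Align 16.4.2 with 3.2.3 by saying how withdrawal samples are summarised. If the 16.4.4 tables were always meant to include the visit before cycle 3, remove the restrictive wording in 16.4.2 and say so.

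The cost is SAP wording and a few table rows from data already collected and listed. No new sample, visit or change to any treatment rule is involved.

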### 16.4.3. ADVERSE EVENTS

All AEs will be assigned to a Preferred Term (PT) and will be classified by primary System Organ Class (SOC) according to the MedDRA thesaurus version 19.1 or higher.

Any AE which started at or after the first administration of study treatment will be considered a Treatment Emergent Adverse Event (TEAE).

Each AE will be graded according to severity definitions as “Mild”, “Moderate” or “Severe”.

Summary of TEAEs will be presented for the SAF set by treatment group.

If the start date is missing for an AE, the AE will be considered to be treatment emergent (See Appendix 2 for more details about how to handle with partial or missing start/stop dates).

TEAEs will be reported on a per-patient basis. This means that even if a patient reported the same event repeatedly (i.e. events mapped to the preferred term) the event will be counted only once.

For summaries, the drug-event relationship will be assessed as “None”, “Unlikely”, “Possible” “Probable” or “Highly probable”. Any TEAE reported in the study having a possible, probable or highly probable relationship to study drug will be defined as “Adverse Drug Reaction” (ADR).

The following tables and listings will be presented:

- 1) An overview of TEAEs including the number of patients who exhibited at least one TEAE, at least one serious TEAE, at least one non-serious TEAE, at least one ADR, at least one serious ADR, number of TEAEs, number of non-serious

---

Document:	MEX0114_SAP_v4_4 Final Methods.docx	Version Number:	Final Version 4.4
Author:	[name]	Version Date:	[17SEP2019]

Template No: CS\_TP\_BS016 – Revision 4  
 Effective Date: 01Apr2016

Reference: CS\_WI\_BS005

TEAEs, number of TESAEs, number of ADRs, number of serious ADRs, number of deaths, number of patients who discontinued study drug due to a TEAE;

- 2) Summary of TEAEs by primary System Organ Class and Preferred Term;
- 3) Summary of TEAEs by primary System Organ Class, Preferred Term and Severity;
- 4) Summary of Serious TEAEs by Primary System Organ Class and Preferred Term;
- 5) Summary of ADRs by Primary System Organ Class and Preferred Term;
- 6) Summary of TEAEs leading to Study Drug Discontinuation by Primary System Organ Class and Preferred Term;
- 7) Summary of TEAEs leading to Death by Primary System Organ Class and Preferred Term;
- 8) Line Listing of all AEs by Patient;
- 9) Line Listing of SAEs by Patient;
- 10) Line Listing of Adverse Drug Reactions by Patient;
- 12) Line Listing of Deaths;

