6.2. DOSE, ROUTE AND SCHEDULE OF IMP ADMINISTRATION

Ladarixin will be administered orally at the dose of 400 mg twice a day for 3 cycles of 14 days on / 14 days off. Placebo will be administered with the same treatment schedule.

The two daily doses will be administered at about 12 hour interval (morning and evening; ideally between 8.30/9.30 and 20.30/21.30). At each administration, 2 capsules will be swallowed with a glass of water, at least 2 hours apart from breakfast or dinner.

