8.2. RECORDING

AE data should be obtained through observation of the patient, from any information volunteered by the patient, or through patient questioning.

All AEs (serious and non-serious) which occur from enrolment through patient participation in the study (last planned visit or early withdrawal date) will be reported and recorded in the CRF. It is important that this includes the duration of the AE (onset/resolution dates), the relationship to the drug, the severity, the outcome and relevant concomitant treatments dispensed (or other action taken).

All AEs should be followed-up to determine outcome of the reaction. The Investigator should follow up the event until resolution or stabilization of the condition. It is the Investigator's responsibility to assure that the subjects experiencing an AE receive definite treatment for any AE, if required.

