## APPENDIX 2. PARTIAL DATE CONVENTIONS

Algorithm for Treatment Emergence of Adverse Events:

START DATE	STOP DATE	ACTION
Known	Known	If start date < study med start date, then not TEAE If start date >= study med start date, then TEAE
	Partial	If start date < study med start date, then not TEAE If start date >= study med start date, then TEAE
	Missing	If start date < study med start date, then not TEAE If start date >= study med start date, then TEAE
Partial, but known components show that it cannot be on or after study med start date	Known	Not TEAE
	Partial	Not TEAE
	Missing	Not TEAE
Partial, could be on or after study med start date	Known	If stop date < study med start date, then not TEAE If stop date >= study med start date, then TEAE
	Partial	Impute stop date as latest possible date (i.e. last day of month if day unknown or 31st December if day and month are unknown), then: If stop date < study med start date, then not TEAE If stop date >= study med start date, then TEAE
	Missing	Assumed TEAE
Missing	Known	If stop date < study med start date, then not TEAE If stop date >= study med start date, then TEAE
	Partial	Impute stop date as latest possible date (i.e. last day of month if day unknown or 31st December if day and month are unknown), then: If stop date < study med start date, then not TEAE If stop date >= study med start date, then TEAE
	Missing	Assumed TEAE

 Document: MEX0114\_SAP\_v4\_4 Final Methods.docx  
 Author: [name]

 Version Number:  
 Version Date:

 Final Version 4.4  
 [17SEP2019]

 Template No: CS\_TP\_BS016 – Revision 4  
 Effective Date: 01Apr2016

Reference: CS\_WI\_BS005

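### The TEAE period has no end date, so TEAE tables 1 to 5 pool about 70 days around dosing with about 42 weeks off drug, and no display by onset period is planned

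*SAP*

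**What the plan says.** SAP 16.4.3 fixes only the start of the treatment-emergent period: "Any AE which started at or after the first administration of study treatment will be considered a Treatment Emergent Adverse Event (TEAE"). The algorithm in SAP Appendix 2 applies the same one-sided rule to known dates: "If start date >= study med start date, then TEAE". Neither gives a date after which an event stops counting.

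Protocol 8.2 collects events "which occur from enrolment through patient participation in the study (last planned visit or early withdrawal date"), and the last planned visit is week 52±2. The endpoint in SAP 3.2.3 covers the same span: "Incidence of Treatment Emergent Adverse Events (TEAEs) and Treatment Emergent Serious Adverse Events (TESAEs) [time frame: throughout the study"].

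Protocol 6.2 sets dosing at "400 mg twice a day for 3 cycles of 14 days on / 14 days off". Protocol 2.5.1 argues that pharmacokinetics in animals and man suggest "clearance of the drug and its metabolites from the body of humans within 2-3 days at the most".

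On counting, SAP 16.4.3 says that "even if a patient reported the same event repeatedly (i.e. events mapped to the preferred term) the event will be counted only once". It plans seven summary tables: an overview (1), then by system organ class and preferred term (2), with severity (3), serious events (4), ADRs (5), events leading to drug discontinuation (6) and events leading to death (7). None is split by time of onset, and no exposure-adjusted rate is planned.

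**The concern.** Safety in this population is a stated objective (Protocol 4.1), and the question closest to the drug is what happens during and shortly after dosing. Protocol 2.5.1 acknowledges that total exposure runs over a longer period than had been explored before in man or animals. Protocol 2.4.3 reports that dyspepsia and dysphagia came soon after administration and that dyspepsia returned with later doses.

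The protocol uses the drug's short persistence elsewhere. Section 3.1 cites pharmacokinetics and reversibility when it places the primary endpoint at week 13. The TEAE tables make no such distinction. For a given preferred term, a placebo patient with one headache at week 40 counts the same as a ladarixin patient with headaches in every cycle. If background events are common, the incidence table can show two similar percentages even though the arms differed clearly during dosing.

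**Working it through.** **1. Length of dosing.** SAP 15.1 gives 168 capsules as the theoretical total. From Protocol 6.2: 2 capsules × 2 per day × 14 days × 3 cycles = 168, which agrees. The last dose therefore falls on day 14 + 14 + 14 + 14 + 14 = 70, with 42 dosing days and two 14-day gaps before it.

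**2. Share of observation time after the last dose.** Formula: (end of follow-up − 70) / end of follow-up.

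- Week 52: (364 − 70)/364 = 294/364 = 80.8%, and 294/7 = 42 weeks.
- Window limits: week 50, 280/350 = 80.0%; week 54, 308/378 = 81.5%.
- Allowing 3 days for clearance: (364 − 73)/364 = 79.9%.
- If the whole 24% drop-out assumed in Protocol 9.1 happened at day 70: 0.76 × 294 / (70 + 0.76 × 294) = 223.4/293.4 = 76%.

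**3. Effect of pooling on per-patient incidence.** The documents give no background rates or event timing, so these inputs are assumed: a constant background rate *h* per patient-year for one preferred term, multiplied by 3 on ladarixin from first dose to week 10 and equal to placebo afterwards. For a window of *w* weeks (10 or more):

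- placebo risk = 1 − exp(−*h* × *w*/52)
- ladarixin risk = 1 − exp(−*h* × (3 × 10 + *w* − 10)/52)

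| *h* per year | Window | Ladarixin | Placebo | Risk ratio | Difference (points) |
|---|---|---|---|---|---|
| 0.5 | 10 weeks | 25.1% | 9.2% | 2.7 | 15.9 |
| 0.5 | 13 weeks | 27.2% | 11.8% | 2.3 | 15.4 |
| 0.5 | 52 weeks | 50.0% | 39.3% | 1.27 | 10.6 |
| 0.1 | 10 weeks | 5.6% | 1.9% | 2.9 | 3.7 |
| 0.1 | 52 weeks | 12.9% | 9.5% | 1.36 | 3.4 |

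The ratio falls sharply in both cases. The difference falls by about a third for the common event (15.9 to 10.6 points) and hardly at all for the rarer one.

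**4. Event counts.** The expected excess at *h* = 0.5 is 0.5 × (3 − 1) × 10/52 = 0.19 events per patient, whichever window is used. An absolute difference in event counts is therefore not diluted. The ratio of event rates is: over 52 weeks a tripled rate appears as (3 × 70 + 294)/364 = 1.38.

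**5. Outputs touched.** Tables 1 to 5 use the open-ended set. Table 6 is in effect limited to the dosing period, because the drug cannot be stopped after its last dose. Laboratory tests and vital signs end at week 13 (SAP 16.4.2), and the last scheduled ECG precedes cycle 3 (SAP 16.5).

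**The case against.** The plan has a good deal in its favour. Counting to week 52 follows the endpoint as stated, and it captures delayed effects that a short window would miss. Dosing-related reactions such as dyspepsia and headache have their own route into the report through the ADR table, with causality judged under double-blinding. Listings show the study day of each event (SAP 7.1), and the overview gives numbers of events as well as patients. Safety is summarised descriptively (SAP 16.4.2), so no power is at stake.

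Most of this stands, and it limits the point to a missing display. Two parts do not fully answer it. The ADR table depends on investigator attribution, which a randomised comparison by period would not need. A listing with study days lets a reader find individual events but does not compare the arms.

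A reader might infer that four fifths of the whole safety comparison is off drug. The documents do not support that: the figure is a share of adverse-event observation time, not of events, and the other safety measures stop at week 13 or earlier. A reader might also infer that a real effect would be hidden. That depends on the assumed background: 0.5 per year implies that 39% of placebo patients report the same term, and nothing in the documents supports that rate.

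**Conclusion.** The gap is real and minor. The TEAE definition has no end, and about 81% of adverse-event observation time behind tables 1 to 5 follows the last dose (80.0% to 81.5% across the visit window). This share rests only on the documents' schedule. An effect confined to the dosing period is diluted on the ratio scale and, for common events, on the difference scale. The amount rests on assumed rates, a constant background and an effect that stops at week 10; the model also carries the raised rate through the two off periods between cycles.

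It would go too far to call the current definition wrong or to replace it, because it matches an endpoint set for the whole study. What is missing is a second display that compares the arms over the period around dosing.

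**What to change.** Keep the 52-week TEAE tables. Add to SAP 16.4.3 a repeat of tables 1 to 5 by onset period:

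- first dose to the week-13 visit, which is the last scheduled laboratory and vital-sign assessment; for patients without that visit, a stated cut-off after the last dose;
- onset after that point.

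The week-13 boundary gives back slightly less contrast than a cut at the last dose (risk ratio 2.3 against 2.7 in the first illustration), but it uses a visit the plan already has.

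Appendix 2 compares dates only with the start of study medication, so it also needs a rule for assigning missing or partial onset dates to one period or the other. Set the cut-off and this rule before unblinding.

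The cost is SAP wording, an onset-date filter on existing programs and more output pages. Data collection and patient management do not change.
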